**Table 2. Table of Study Procedures**

	3-month Observation			12-month Treatment Phase					
	Obs-V1 Baseline	Obs-V2 2-mo	Obs-V3 3-mo	Tx-V1 Baseline	Tx-V2 1-mo	Tx-V3 3-mo	Tx-V4 6mo	Tx-V5 9-mo*	Tx-V6 12-mo
Timeline in Weeks (range of days)	Week 0 (Day 0)	Week 9 (51-63)	Week 12 (84-96)	Week 12-15 (84-105)	Week 21 (141-153)	Week 26 (176-188)	Week 38 (260-272)	Week 50 (344-356)	Week 64 (441-454)
Informed consent	X								
Inclusion/Exclusion Criteria	X								
Collection of demographic data	X								
Medical History	X								
Physical Exam	X		X		X	X	X	X	X
Functional status/NYHA class	X		X		X	X	X	X	X
QOL Minnesota HF Questionnaire	X		X		X	X	X	X	X
Current / change of medications	X		X		X	X	X	X	X
12-lead ECG	X*	X*	X		X*	X*	X*	X*	X*
Ziopatch	X	X ‡			X €	X	X		X
Echo	X £		X ‡			X	X*		X
BNP / ProBNP levels ESR & CRP	X* £		X*		X*	X*	X*	X*	X*
Urine pregnancy test (if applicable)	X		X	X	X	X	X	X	X
CMR	X*								
TSH (if assigned to amiodarone)			X				X		X
LFT (AST) (if assigned to amiodarone)			X				X		X
Treatment randomization	X								
Initiation of RFA or ADD				X					

Collection of unsolicited AEs	From Obs-Visit 1 until Tx-Visit 6
--------------------------------------	-----------------------------------

Footnote: \*, visit/intervention if clinically indicated.

‡ LVEF results of 2D-echocardiogram and Ziopatch have to be available at the time of Observation Visit 3 (Obs-V3). € If PVC burden >10%, subject should be considered to either adjust antiarrhythmic therapy (AAD group) or second ablation procedure (RFA group) based on their randomization group. ESR, Erythrocyte sedimentation rate; CRP, C-reactive protein. £ Must be done within 150 days of Enrollment Visit (Day 0)

Crossover between PVC suppression strategies is not encouraged. We request that crossover only be considered after 6 months of initiation of treatment, for which an intention-to-treat analysis will be performed. However, if crossover occurs before 6 months of initiation of treatment, subjects will be withdrawn from the study and included in the PVC-CM registry if the subject provided consent.

Every effort will be made to have females enter this study. Medically accepted birth control is required to enter this study. This may include, but is not limited to, birth control pills, IUD's, condoms, diaphragms, implants, being surgically sterile, or being in a post-menopausal state. However, no birth control method completely eliminates the risk of pregnancy and potential risk of miscarriage, birth defects, other medical complications or unforeseen risks to subject or to the unborn baby (i.e. embryo or fetus) is possible if pregnancy occurs during the study. Any female of childbearing age must have a negative pregnancy test before entering the study.

A pregnancy test will be obtained on females of childbearing age that are assigned to the RFA treatment prior to procedure due to fluoroscopy exposure. In contrast, a pregnancy test will be performed on a monthly basis on those randomized to the antiarrhythmic treatment arm to confirm the lack of pregnancy throughout the 12-month follow up. If a female on the antiarrhythmic arm becomes pregnant during the 12-month follow up we will consider stopping antiarrhythmics and the subject will be withdrawn from the study.

Thus, subjects that no longer meet criteria after the 3-month observation period, those that crossover before 6 months of treatment initiation or become pregnant during the study will be included in the PVC-CM registry if the subject provided consent. Subjects that refuse participation in this portion of the study (Part I) will also be included in the PVC-CM registry if they provide consent.

**A.1. PVC-CM registry.** This registry will consist of patients that: 1) refuse to participate in the randomized treatment protocol, 2) no longer meet criteria after 3-month observation, 3) crossover before 6 months of treatment initiation, or 4) become pregnant during the study. When allowed by the IRB, informed consent will include an option for participation in this registry as a contingency in case subjects no longer meet criteria, become pregnant, crossover treatment arms or decide to withdraw from the study. A separate informed consent to participate in this registry will be provided only for those patients that refuse participation in the randomized treatment study (main study). Data will be collected at Baseline (day subject refuses enrollment in the randomized study), 6 and 12 months for these subjects. Alternately, subjects included in this PVC-CM registry who screen fail or withdraw early for any reason, will have data collected only by chart review at 6 and 12 months after withdrawing from the study. Data to be collected will include demographics, past medical history, treatment interventions including outcomes and related complications, NYHA functional status, 12-lead ECG, ambulatory ECG Holter including heart rate, PVC burden and arrhythmia burden, echocardiographic data including LVEF, medications and cardiac-related hospital admissions. The purpose of this registry is to assess different treatment options offered to patients with this medical condition in the “real world” as well as the clinical response to these treatments.

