Additional Endpoint(s)	
 
1. Efficacy of RFA vs AADs groups to achieve successful PVC suppression at 12-month follow-up, defined as a reduction of PVC burden ≥80% (regardless of LVEF change). Understanding the success rate of PVC suppression between RFA and AADs will help better determine the best treatment to those subjects with high PVC burden.
 
2. Composite end-point of adverse events at 12-month follow-up, including worsening in NYHA functional class (I-IV), number of HF and cardiac-related admissions, RFA complications and AAD adverse effects and cardiovascular death.
 
3. Composite end-point of arrhythmia burden at 12-month follow-up, including PVC recurrence, non-sustained (< 30sec) and sustained (> 30sec) ventricular arrhythmias and arrhythmic sudden cardiac death.
 

Follow up Schedule
	
Subjects will be screened via chart review. If the inclusion criteria is met, subject will be asked to participate in the study during Visit 1 (Week 0)  Each enrolled subject will be followed at the following visits:
 
 
- Week 0 –, Enrollment, informed consent and clinical evaluation
 
- Week 9 – ECG and ambulatory ECG recording
 
- Week 12 – Clinical evaluation and echocardiogram
 
- Week 12-15 – Initiation of intervention (RFA or AADs)
 
- Week 21 – Clinical evaluation
 
- Every 3 months after RFA or AADs (week 38, 50 and 64) – Clinical assessment with occasional testing (echocardiogram and ambulatory ECG recording)
 
- Week 64 – Complete protocol.
 
 
All visits and testing are clinically indicated and considered standard of care. Most of these subjects receive this follow up regardless of participation in the study.

Study Duration
	
Study duration is approximately 36 months.  Each subject will be followed for at least 15 months, which includes a 3-month observation period and 12months after intervention is initiated.
 
 
- Enrollment and subject follow up of all subjects is estimated to be completed within 3 years.
 

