**Definitions:**

The *diagnosis criteria for PVC-CM* is based on LVEF  $\leq$  45% (by echocardiography) and average PVC burden  $\geq$  10% in an ambulatory ECG Holter monitor that meet the inclusion and exclusion criteria (Table 1), regardless of severity and time of onset. LVEF and PVC burden must be within 150 days of Enrollment Visit (Day 0).

*Responders are defined as an LVEF increase greater than 10% points regardless of intervention.*

If screening confirms eligibility (LVEF  $\leq$ 45% and PVC burden  $\geq$  10%), a baseline visit will be scheduled to obtain subject's demographics and medical history, 12-lead ECG, Minnesota living with HF quality of life (QOL) questionnaire, NYHA functional class and cardiac magnetic resonance (CMR) if clinically indicated. Subjects that refuse enrollment, will be asked to participate in a PVC-CM registry to follow their response and crossover to different treatment strategies.

If subjects meet inclusion criteria (Table 1) during screening, informed consent should be obtained. Stratified randomization to either RFA or AADs will be performed at the time of enrollment (baseline visit, week 0). Based on our preliminary data, we expect that around 30% of subjects will have a PVC burden  $>$ 20%. Thus, a *stratified randomization based PVC burden (assessed by Holter) above and below 20% is needed to assure that subjects in both groups (RFA vs. AAD) are equally distributed between PVC burden above and below 20%.* Stratified randomization will be performed using approved software available at the Coordinating Center only.

If a subject is randomized to the RFA arm, a RFA procedure (Visit 1) should be scheduled at the time of randomization due to usual 8-week next available RFA appointment in most participating centers. Yet both, RFA and AAD interventions should only occur or be initiated after completion of a 3-month observation (Table 2 - Visit Tx-V1, week 12-15).

A 3-month observation period will assess spontaneous variation of PVC burden and improvement or deterioration of LV function. During the final 3-month observation visit (Week 12), LVEF and Holter will be repeated to confirm eligibility if PVC burden and LVEF remains  $\geq$ 10% and  $\leq$ 45%, respectively.

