iii. *Observation – Visit 3.* Similar to Visit 1, appropriate data collection forms should be used to collect current medical therapy, NYHA functional class and Minnesota HF quality of life questionnaire (QOL). 12-lead ECG should be obtained if clinically indicated. Transthoracic echocardiogram should be performed to assess LVEF and a copy mailed to the Echo Core laboratory led by [name] III, M.D. The local PI and designated site staff will be able to log in to iRhythm's ZioReports to obtain the Zio Patch report that should include a 2-week PVC burden.

[figure not shown]
If PVC burden remains  $\geq 10\%$  and LVEF  $\leq 45\%$ , then the subject will either initiate antiarrhythmic drugs or undergo RFA procedure (see Section C: Description of the intervention/treatment) and will continue on protocol as scheduled. However, if these criteria are no longer met, the subject is considered a screen failure and is withdrawn from the study. In such a case, the treatment decision is solely at the discretion of the electrophysiologist caring for subject. Nevertheless, this subject will be included in a PVC-CM registry if consent was provided (described above Section A.1).

i) *Treatment – Visit 1.* This is considered the baseline visit where PVC suppression strategy assignment is initiated (either RFA or AADs). If the subject is randomized to RFA, we will request that sites complete the RFA data collection form which includes information during the RFA procedure as well as recovery, complications and hospital stay. EPS will be performed on their baseline medications, except for antiarrhythmic drugs class II (beta blockers) which will be held at least 5 half-lives prior to procedure. Beta blockers should be resumed after RFA.

iv. However, subjects randomized to AADs can have this visit combined with Observation-Visit 3. In addition, subjects in the antiarrhythmic (AAD group) will require a baseline TSH and LFTs (AST only) if amiodarone is chosen.

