#### *Rate of responders to PVC suppression*

Besides improvement in LV systolic function, no study has been designed to demonstrate clinical benefits with either RFA or AADs. Clinical benefits are implied based solely on the improvement of LVEF. Based on prior retrospective and observational studies, the rate of responders (improvement of LVEF) to PVC RFA is estimated at 50-65%. Unfortunately, there is no recent data on antiarrhythmics due to the lack of recent studies. Our preliminary data from the CHF-STAT study demonstrates a response rate of 28% (Preliminary Data Section).

We plan to further identify the rate of responders after PVC suppression by obtaining the following primary end-points: 1) improvement in LVEF (determined by  $\Delta \text{LVEF} = \text{final LVEF} - \text{baseline LVEF}$ ) and 2) “responders” to PVC suppression (defined as change in LVEF  $\geq 10\%$ ). In addition, we will obtain QOL and NYHA functional class questionnaires (secondary end-point described above). Each subject will serve as its own control, since all data obtained will be compared between the end of 3-month observation period (control phase - prior to randomization) vs. 3-month after PVC suppression strategy, regardless of treatment randomization (RFA and AAD). We hypothesize that a PVC suppression strategy (RFA or AAD) is better than optimal HF medical therapy alone to improve LV function, HF symptoms, heart failure admissions, and avoid the need for defibrillator. *The PAPS pilot study will help us determine the rate of responders to PVC suppression strategy in order to properly estimate sample size and power the large randomized PAPS study.*

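### Table 2 counts post-treatment visits from enrolment although treatment may start on any day from 84 to 105, so the 12-month visit falls 336 to 370 days after treatment and reaches 365 days only for starts by day 89

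*Combined protocol and SAP*

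**What the plan says.** Table 2 sets enrolment as Day 0 and gives each later visit as a range of days from it. Treatment start (Tx-V1) is "Week 12-15 (84-105", and the final visit, labelled 12-mo, is "Week 64 (441-454". The Definitions paragraph applies the same start window to both arms: "RFA and AAD interventions should only occur or be initiated after completion of a 3-month observation (Table 2 - Visit Tx-V1, week 12-15".

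The Protocol Synopsis (Study Duration) describes the follow-up differently: "Each subject will be followed for at least 15 months, which includes a 3-month observation period and 12months after intervention is initiated". Its Follow up Schedule combines both clocks in one line, "Every 3 months after RFA or AADs (week 38, 50 and 64", and leaves out the week-26 visit that Table 2 lists as Tx-V3.

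Section B (Scheduled Visits) states that "subjects randomized to AADs can have this visit combined with Observation-Visit 3", whose window is days 84 to 96. For RFA it asks for a procedure booked three months from enrolment. Section D times the first suppression Holter at 4-6 weeks after the ablation or the start of drug, whereas Table 2 and Section B place that Holter at Tx-V2 (days 141 to 153). The notes under Table 2 count the 6-month crossover limit from initiation of treatment. No section ties the later windows to the actual treatment date, and Section I (Statistical analysis) does not mention time since treatment.

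**The concern.** Both primary endpoints are defined at 12 months of follow-up after PVC suppression. If the calendar runs from enrolment while treatment can begin anywhere in a three-week span, the time since treatment at a given visit depends on the start day. A late starter then cannot have the stated 12 months of follow-up without missing the visit window.

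The same anchoring affects two other rules that the protocol does count from treatment: the timing of the first suppression check, and the 6-month boundary that decides whether a crossover leads to withdrawal or to retention under intention-to-treat. The pilot is meant to supply response and crossover rates for the larger trial, so an inconsistent clock would be carried forward.

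**Working it through.** **Inputs (Table 2, days from enrolment).** Tx-V1 84-105; Obs-V3 84-96; Tx-V2 141-153; Tx-V3 176-188; Tx-V4 260-272; Tx-V6 441-454.

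**The plan's own label.** Week 64 is 64 × 7 = day 448, and 448 − 84 = 364 days. The 12-month label thus reproduces for a start on the first permitted day. For a start on day 105 it gives 448 − 105 = 343 days.

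**Time since treatment = visit day − start day.**

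| Visit | Start day 84 | Start day 96 | Start day 105 | Overall |
|---|---|---|---|---|
| Tx-V2 (1-mo) | 57-69 | 45-57 | 36-48 | 36-69 |
| Tx-V3 (3-mo) | 92-104 | 80-92 | 71-83 | 71-104 |
| Tx-V4 (6-mo) | 176-188 | 164-176 | 155-167 | 155-188 |
| Tx-V6 (12-mo) | 357-370 | 345-358 | 336-349 | 336-370 |

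**Starts that can reach 365 days.** 454 − 365 = day 89, so days 84-89 qualify: 6 of 22. The other 16 cannot reach 365 days in window.

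**Suppression Holter.** Six weeks is 42 days, and 141 − 42 = day 99. Only starts on day 99 or later can have the Tx-V2 Holter placed within 42 days. Reaching 365 days at Tx-V6 needs day 89 or earlier. No permitted start day satisfies both, and days 90-98 satisfy neither.

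**Crossover boundary.** Taking 6 months as 182 days, 272 − 182 = day 90. For any start after day 90 the whole Tx-V4 window lies before 6 months of treatment, so a crossover at the visit labelled 6-mo could count as early.

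**What anchoring adds.** The start window spans 105 − 84 = 21 days. The full spread at Tx-V3 is 104 − 71 = 33 days, but 188 − 176 = 12 of those are ordinary visit tolerance that would remain under any anchoring.

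**Possible effect on LVEF (assumption).** The documents give no LVEF trajectory over these weeks. Assume a gain of 15 × (1 − exp(−t/T)), where 15 points is the planned RFA change (25% to 40%) and T is 60, 90 or 120 days.

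- *3 months, 21-day shift.* t = 92 against 71 gives 1.36, 1.42 and 1.33 points; t = 104 against 83 gives 1.11, 1.24 and 1.21. The range is about 1.1 to 1.4.
- *12 months, permitted extremes.* t = 370 against 336 gives 0.024, 0.113 and 0.225 points.

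For scale, with 18 subjects per arm and SD 10 the standard error of the arm difference is 10 × √(2/18) = 3.3 points, so 0.225 is under 7% of one standard error.

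**Sample size.** A 5-point difference, SD 10, two-sided 0.05 (sidedness assumed) and 80% power give 63 per arm. Then 63/0.9 = 70 per arm, or 140, as stated. Visit timing does not enter this figure.

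**The case against.** The strongest reply is that the consequence is slight. Part I is a feasibility pilot, follow-up is elsewhere described as only approximately three-monthly, treatment details are recorded so elapsed time can be reported, and the 12-month effect is negligible beside the planned 5-point difference. That stands, and it limits the severity. It does not remove the contradiction between the synopsis and Table 2.

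A reader might infer more than the documents support:

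- *That RFA follow-up is systematically shorter.* Drug start may be merged with Obs-V3 (345-370 days at Tx-V6), while RFA is a booked procedure (336-370 days), so a gap could arise. But both arms share the day 84-105 window, RFA is requested at three months, and merging is optional for the drug arm. Neither a systematic gap nor its size can be established.
- *That the own-control comparison is confounded by arm.* Section F makes it against the value "3-month after PVC suppression strategy, regardless of treatment randomization (RFA and AAD", so it pools the arms. Start-day spread adds noise to the 3-month value, not an arm effect.
- *That every window fits its label only near day 84.* This is untrue for Tx-V3: its window contains day 91 of treatment for starts on days 85 to 97 (176 − 91 and 188 − 91).
- *That the schedule of echocardiograms shows recovery continuing at 3 months.* A visit schedule is not evidence of a trajectory.

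**Conclusion.** The inconsistency is real and follows from Table 2's own day ranges. The 12-month visit falls 336 to 370 days after treatment, and 16 of 22 permitted start days cannot deliver the 12 months stated in the synopsis. The same clock cannot be squared with the 4-6 week Holter, and it places the 6-month visit before the crossover boundary for starts after day 90. Up to 21 days of variation in time since treatment come from the anchoring alone.

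Bias in the primary 12-month contrast is likely small, at most about 0.2 LVEF points between permitted extremes. A 21-day shift at 3 months would be worth about 1.1 to 1.4 points. Both LVEF figures compare individuals at different times since treatment, not arm means, and rest wholly on the assumed exponential curve. An arm difference in timing is possible, not shown. Severity: minor.

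**What to change.** In Table 2 and the synopsis, count the Tx-V3 to Tx-V6 assessment windows (clinical, echo, Zio) from the actual treatment start at Tx-V1, keeping the present widths. For example, centre the 3-month echo on Tx-V1 + 91 days and the 12-month echo and Zio on Tx-V1 + 365 days. Even keeping the present offset from day 84 (357-370 days after Tx-V1) would narrow the 12-month range from 336-370 to 357-370 days; a day-105 starter would then be seen on study days 462-475.

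Reconcile the Tx-V2 timing in Table 2 and Section B with the 4-6 weeks in Section D, and the Tx-V4 window with the 6-month crossover clock. Which clinical rule should govern is for the investigators. Add the week-26 visit to the synopsis list as an editorial correction.

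The cost is an amendment to one table and the synopsis, plus a REDCap window calculated from the treatment date. Last visits move by up to about three weeks for late starters. No visits or tests are added.
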